- Other known causes of ILD include conditions such as systemic sclerosis, rheumatoid arthritis, systemic lupus erythematosus, dermatomyositis, polymyositis, Sjögren disease, and hypersensitivity pneumonitis (ICD-9-CM codes 135, 237.7, 272.7, 277.3, 277.8, 446.21, 446.4, 495, 500–505, 506.4, 508.1, 508.8, 516.0, 516.1, 516.32–516.37, 516.2, 516.8, 516.9, 517.0, 517.2, 517.8, 518.3, 555, 710.0, 710.0–710.4, 714.0, 714.81, 720, and 759.5, or ICD-10-CM equivalent codes)^{12,13}
- With ≥ 1 prescription for nintedanib prior to the index date
- With ≥ 1 prescription for pirfenidone prior to or on the index date

Pirfenidone cohort

Inclusion criteria:

- With ≥ 1 diagnosis for IPF (ICD-9-CM codes 516.3, 516.31, 515,¹¹ or ICD-10-CM codes J84.112) in the EMR between October 1, 2013 to April 30, 2018
- With ≥ 1 prescription for pirfenidone between October 1, 2014 and April 30, 2018 (the selection window)
 - The date of the first prescription will be defined as the index date
- With ≥ 1 record in the EMR database during the 12 months prior to the index date
- With ≥ 1 diagnosis of IPF during the 12 months prior to the index date
- Age ≥ 40 on the index date
- will explore also requiring ≥ 1 chest CT scan before first IPF diagnosis during the pre-index period¹²

Exclusion criteria:

- With ≥ 1 diagnosis of other known causes of interstitial lung disease (ILD) on the date of or after the first IPF diagnosis during the pre-index period^{12,13}
 - Other known causes of ILD include conditions such as systemic sclerosis, rheumatoid arthritis, systemic lupus erythematosus, dermatomyositis, polymyositis, Sjögren disease, and hypersensitivity pneumonitis (ICD-9-CM codes 135, 237.7, 272.7, 277.3, 277.8, 446.21, 446.4, 495, 500–505, 506.4, 508.1, 508.8, 516.0, 516.1, 516.32–516.37, 516.2, 516.8, 516.9, 517.0, 517.2, 517.8, 518.3, 555, 710.0, 710.0–710.4, 714.0, 714.81, 720, and 759.5, or ICD-10-CM equivalent codes)^{12,13}
- ≥ 1 prescription for pirfenidone prior to the index date
- ≥ 1 prescription for nintedanib prior to or on the index date

Untreated cohort

Inclusion criteria:

- With ≥ 1 diagnosis for IPF (ICD-9-CM codes 516.3, 516.31, 515,¹¹ or ICD-10-CM codes J84.112) in the EMR between October 1, 2013 to April 30, 2018
 - Index date will be defined as the date of the earliest IPF diagnosis or a randomly assigned date based on the exploratory analyses to be performed on the two treatment cohorts (exploring time from IPF diagnosis to treatment initiation)

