- Charlson comorbidity index (CCI)¹⁵ (mean, SD, median, min, max) and categories (n, %), defined using ICD diagnosis codes
 - 0
 - 1
 - 2
 - 3
 - 4+
- Respiratory comorbidities¹⁶ (n, %), defined using ICD diagnosis codes
 - COPD (Chronic obstructive pulmonary disease), includes chronic bronchitis and emphysema
 - Pulmonary hypertension
 - Obstructive sleep apnea
 - Lung cancer
 - Pulmonary embolism
 - Asthma
 - Acute respiratory distress syndrome
 - Pulmonary edema
 - Cough
 - Upper respiratory tract infection (includes acute bronchitis)
 - Bronchitis (not specified as acute or chronic)

- Sinusitis
- Gastroesophageal reflux disease (GERD) (n, %), defined using ICD diagnosis codes
- Metabolic disorders¹⁶ (n, %), defined using ICD diagnosis codes
 - Obesity (defined as ICD-9 code 278.0 or ICD-10 code E66 or BMI ≥ 30 kg/m²)
 - Diabetes
 - Any diabetes
 - Type 1 diabetes
 - Type 2 diabetes¹⁶
 - Dyslipidemia (includes hypercholesterolemia and hyperlipidemia)
- Cardiovascular disorders¹⁶ (n, %), defined using ICD diagnosis codes
 - Arrhythmia
 - Atrial fibrillation
 - Heart failure
 - Ischemic heart disease
 - Stroke
 - Hypertension (includes systemic arterial hypertension)
 - Peripheral arterial diseases
 - Cardiomyopathy
- Mental disorders (n, %), defined using ICD diagnosis codes
 - Depression
 - Anxiety
 - Schizophrenia
 - Dementia
 - Bipolar disorders
- Renal impairment (n, %), defined using ICD diagnosis codes
- Hepatic impairment (n, %), defined using ICD diagnosis codes
- Laboratory measures (to the extent that the data allow; tests will be identified by procedure codes and EMR data fields; if repeated measurements of a test are observed, the one closest to the index date will be reported, with the exception of several renal and liver measures (where noted) when any evidence of patient history of the condition during baseline will take precedent over the measure closest to index)
 - Anticoagulation tests (n, %)
 - Prothrombin time (n, %)
 - High (>14 seconds)
 - Normal (10-14 seconds)
 - Low (<10 seconds)
 - Activated partial thromboplastin time (aPTT; n, %)
 - Normal (30-40 seconds)
 - Elevated (41-70 seconds)

- Critical (>70 seconds)
- Bleeding time (n, %)
 - Normal (1-9 minutes)
 - Platelet dysfunction (10-15 minutes)
 - Critical (>15 minutes)
- Hematologic markers
 - Blood hemoglobin (mean, SD, median, min, max)
 - Blood hematocrit (mean, SD, median, min, max)
 - Red blood cell count (mean, SD, median, min, max)
 - Platelet count (n, %)

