 - Low (<150,000 platelets/mcL)
 - Normal (150,000-450,000 platelets/mcL)
 - High (>450,000 platelets/mcL)
 - Conventional C - reactive protein (n, %)
 - Normal (≤ 5.0 mg/L)
 - High (>5.0 mg/L)
- Liver function tests (n, %)
 - Alanine transaminase (ALT; n, %); patient history of high ALT level suggesting hepatic impairment will be reported and take precedent to ALT value closest to index
 - Low (<7 U/L)
 - Normal (7 – 56 U/L)
 - High (>56 U/L)
 - Aspartate transaminase (AST; n, %); patient history of high AST level suggesting hepatic impairment will be reported and take precedent to AST value closest to index
 - Low (<5 U/L)
 - Normal (5 – 40 U/L)
 - High (>40 U/L)
 - Alkaline phosphatase (ALP; n, %)
 - Low (<44 IU/L)
 - Normal (44 – 147 IU/L)
 - High (>147 IU/L)
 - Gamma-glutamyl transpeptidase (GGT; n, %)
 - Low (<9 U/L)
 - Normal (9-48 U/L)
 - High (>48 U/L)
 - Total bilirubin (n, %); patient history of high bilirubin level suggesting hepatic impairment will be reported and take precedent to value closest to index
 - Low (<0.2 mg/dL)

- Normal (0.2-1.2 mg/dL)
 - High (>1.2 mg/dL)
 - Kidney function tests (n, %)
 - Albumin to creatinine ratio (ACR; n, %)
 - Normal (<30)
 - Microalbuminuria (30-300)
 - Macroalbuminuria (>300)
 - Glomerular filtration rate (GFR; n, %); patient history of low GFR suggesting renal impairment will be reported and take precedent to value closest to index
 - Low (<90 mL/min/1.73m²)
 - Normal (90 – 120 mL/min/1.73m²)
 - High (>120 mL/min/1.73m²)
 - Serum creatinine (mean, SD, median, min, max); patient history of high serum creatinine level suggesting renal impairment will be reported and take precedent to value closest to index
 - Cholesterol levels (n, %)
 - Total cholesterol (mg/dL; n, %)
 - Normal (<200 mg/dL)
 - Borderline high (200-239 mg/dL)
 - High (\geq 240 mg/dL)
 - Triglyceride (mg/dL; n, %)
 - Normal (<150 mg/dL)
 - Borderline high (150-199 mg/dL)
 - High (\geq 200 mg/dL)
 - Cholesterol in high-density lipoprotein (HDL; n, %)
 - Normal (\geq 40 mg/dL)
 - Abnormal (<40 mg/dL)
 - Cholesterol in low-density lipoprotein (LDL; n, %)
 - Normal (<100 mg/dL)
 - Borderline high (100 – 159 mg/dL)
 - High (\geq 160 mg/dL)
- Pulmonary function tests (PFTs) indicative of IPF severity (n, %)
 - FVC (n, %)
 - Normal (\geq 80%)
 - Abnormal (<80%)
 - Forced expiratory volume in one second (FEV1) /FVC ratio (n, %)
 - Normal (\geq 70%)
 - Abnormal (<70%)
 - Total lung capacity (TLC) (mean, SD, median, min, max)

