9.7.1 Main analysis

For the primary objective, baseline patient characteristics will be described using descriptive analysis, i.e. described as counts and percentages for categorical variables (e.g. gender, race, comorbidities, treatments, diagnostic tests performed) and measures of central tendency (mean, median, SD, and min/max) for continuous variables (e.g., age, lab measures values, BMI). Differences between the cohorts will be assessed using ASD, where an ASD of at least 10% will be considered a meaningful difference.²² Patients with missing data will be reported as missing and excluded from the comparison for the missing variable.

For continuous variables, the standardized differences will be calculated as

$$d = \frac{(\bar{X}_1 - \bar{X}_2)}{\sqrt{\frac{s_1^2 + s_2^2}{2}}}$$

Where \bar{X} denote sample means in each exposure cohort, and s denotes sample variances.

For categorical variables, the standardized differences will be calculated as

$$d = \frac{(p_1 - p_2)}{\sqrt{\frac{[p_1(1 - p_1) + p_2(1 - p_2)]}{2}}}$$

Where p denotes proportion of a binary baseline variable in the two exposure cohorts.

The confidence intervals (CIs) for standardized differences will also be calculated as defined below:

$$95\% CI = d \pm 1.96 \times \sigma [d]$$

$$\text{where, } \sigma [d] = \sqrt{\frac{n_1 + n_2}{n_1 \times n_2} + \frac{d^2}{2(n_1 + n_2)}},$$

Where n_i denotes sample sizes of each exposure cohort.

Bivariate statistical significance tests such as Chi-square test for categorical variables and Wilcoxon rank sum test or t-test for continuous variables (depending on distribution of data) will also be performed to compare differences in baseline characteristics between the three cohorts. In addition to standardized differences, p-value in comparing characteristics between the three cohorts will also be reported to help identify “key drivers” associated with treatment selection.

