For the second objective, the probabilities of receiving one treatment over another (or nintedanib or pirfenidone vs. untreated) will be tested by propensity scores (PS) and using multivariable logistic regression (possibly with stepwise selection) after controlling for key baseline characteristics (selected based on significance in bivariate analysis or face validity, e.g. age). The similarities and differences between the exposure cohorts will be assessed using balance diagnostics tests (e.g., graphical distribution of overlap between propensity scores of two cohorts (histograms, boxplots), percentage of sample matched, Pearson’s correlation coefficient, standardized differences, density estimates, c-statistics, receiver operating characteristic [ROC] curves). Ninety-five percent confidence intervals will be calculated for key parameters. Statistical tests will be two-sided, with α -level of 0.05 for statistical significance.

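### Serum creatinine is summarised as a mean and SD but carries an any-history override with no limit for a high value, so on the natural reading the row mixes closest-to-index values with selected earlier highs.

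*Combined protocol and SAP*

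**What the plan says.** Section 9.3.3 (Laboratory measures) sets a default for repeated tests: the value closest to the index date is reported. Certain renal and liver measures are exempt, "when any evidence of patient history of the condition during baseline will take precedent over the measure closest to index". The exemption is then attached to five tests.

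- ALT: "patient history of high ALT level suggesting hepatic impairment will be reported and take precedent to ALT value closest to index". AST and total bilirubin carry parallel wording.
- GFR: "patient history of low GFR suggesting renal impairment will be reported and take precedent to value closest to index".
- Creatinine: "Serum creatinine (mean, SD, median, min, max); patient history of high serum creatinine level suggesting renal impairment will be reported and take precedent" over the closest value.

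The first four are reported as n (%) in printed categories: ALT high above 56 U/L, AST high above 40 U/L, bilirubin high above 1.2 mg/dL, GFR low below 90 mL/min/1.73m². Creatinine has no categories and no limit.

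The only separate renal-history row in the list is "Renal impairment (n, %), defined using ICD diagnosis codes", which does not use laboratory values. Section 9.7.1 plans means and SDs "for continuous variables (e.g., age, lab measures values, BMI"), and builds the standardized difference for continuous variables from cohort means and variances.

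**The concern.** An override by history works for a category: a patient with any ALT above the limit is counted as high, and the row has a clear meaning. It does not carry over to a mean. If an earlier high creatinine displaces the value closest to index, some patients contribute their renal function near index and others contribute a value selected for being high. The summary then describes neither renal function at index nor history of impairment. It also depends on how often patients were tested and on a cut-off the plan does not state.

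Two programmers could follow the plan and report different means from the same records. The row could not be read alongside hemoglobin, hematocrit or red cell count, which use the closest value. Describing baseline characteristics is part of the primary objective (Section 8). Covariates for the second-objective model may be "selected based on significance in bivariate analysis or face validity", so the variable needs a single definition.

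**Working it through.** **Text check.** The five override tests side by side:

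| Test | Summary | Limit printed | Effect of override |
|---|---|---|---|
| ALT | n, % | >56 U/L | moves the patient to a defined category |
| AST | n, % | >40 U/L | same |
| Total bilirubin | n, % | >1.2 mg/dL | same |
| GFR | n, % | <90 mL/min/1.73m² | same |
| Serum creatinine | mean, SD, median, min, max | none | substitutes a number, by an undefined rule |

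Annex 1 describes its stand-alone files as procedure, diagnosis and medication codes, not laboratory limits. The files themselves are not part of the documents.

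**Size.** The plan states no creatinine mean, SD or test count, so there is no figure to reproduce. Everything below rests on assumptions: standardised normal values, correlation ρ between a patient's tests of 0.5-0.8, a share p of values called high of 5-20%, and the same number of tests for everyone. Let c be the (1−p) quantile and φ the normal density.

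*Two tests, latest high value used.* Let X1 be the value closest to index and X2 the earlier one. Substitution occurs only when X1 ≤ c < X2, so

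shift = E[(X2−X1); X2>c] − E[(X2−X1); both>c] = (1−ρ)φ(c) − 0.

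- p = 5%: c = 1.645, φ(c) = 0.1031. With ρ = 0.8 the shift is 0.2 × 0.1031 = 0.021 SD.
- p = 20%: c = 0.842, φ(c) = 0.2800. With ρ = 0.5 the shift is 0.5 × 0.2800 = 0.140 SD.

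*Other cases, by simulation (1,000,000 patients per setting):*

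| Tests per patient | High value used | Rise in mean (SD units) | Values replaced |
|---|---|---|---|
| 2 | latest | 0.02-0.14 | 2.5-11% |
| 2 | highest | 0.03-0.16 | 4-16% |
| 4 | latest | 0.05-0.31 | 6-24% |
| 4 | highest | 0.06-0.38 | 8-33% |

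With the highest value used, the SD rises by 4-11% (two tests) or 9-20% (four). The median rises by 0.00-0.13 SD with two tests, and by at most 0.03 at ρ = 0.8.

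*Sensitivity.* At ρ = 0.9 the rise in the mean falls to 0.02-0.05 SD (two tests) and 0.03-0.11 (four), highest value used. With right-skewed values (coefficient of variation 0.4) it grows to 0.04-0.20 and 0.10-0.48.

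*Effect of the unstated cut-off.* Same patients, 5% versus 20% called high, highest value used: the means differ by 0.06-0.11 SD (two tests) and 0.12-0.24 (four). With the latest high value and two tests, the difference is (1−ρ)(0.2800−0.1031), or 0.035-0.088.

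*In mg/dL.* A second model assumed log-normal values with median 0.95, between-patient log-SD 0.25, four tests and a limit of 1.3 or 1.5. With within-patient log-SD 0.10, the mean moves from about 0.985 to 0.996-1.018. With log-SD 0.20, it moves from about 1.00 to 1.06-1.11. The ranges cover both choices of high value.

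**Effect on the ASD.** If cohorts are tested equally often and have the same creatinine distribution, the rule adds the same amount to both means, so a true difference of 0 stays 0. A true standardized difference of 0.10 becomes 0.099-0.111 in simulation.

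**The case against.** The strongest reply is that a separate history item was meant. The creatinine line does say that the history will be reported, the parent line for kidney function tests carries n (%), and the general rule speaks of evidence of a condition, which is a status and not a number to average. This reading is possible, so the mixing is the natural reading and not a certainty. But precedence over the closest value points to substitution, and a separate item would still lack both a limit and a row. Either reading needs a change to the text.

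It can also be said that renal status is covered elsewhere (ICD-coded impairment, GFR with a limit, albumin to creatinine ratio), that one row in a long list is affected, and that Section 9.6 requires review of the programming code. The first two are correct and limit the importance. Code review does not supply a rule that the plan leaves out.

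Two stronger readings are tempting. A reader might infer that the rule creates false differences between treated and untreated patients. That requires unequal testing: under the same kind of assumptions, an average gap of one test gives a creatinine ASD of 0.02-0.12. The documents report no test counts and show no such gap, between treated and untreated or between the two drugs. A reader might also infer that the rule is wrong for ALT, AST, bilirubin and GFR. It is not: with printed limits, any-history classification is a legitimate definition.

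**Conclusion.** The point holds for serum creatinine only. A rule suited to categories is attached to a continuous summary, with no limit for a high value and no choice among several highs. On the natural reading, the mean and SD are biased upward: about 0.02-0.16 SD in the mean with two tests per patient and 0.05-0.38 SD with four, if within-patient correlation is 0.5-0.8 and 5-20% of values are high. These inputs are assumptions. At correlation 0.9 the effect is small, and with skewed values it is larger.

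The harm is to one descriptive row and to its reproducibility. With equal testing the between-cohort ASD is practically unchanged, and no study conclusion is shown to be at risk. The change should still be made, because the rule is unsuited to the summary and costs little to correct.

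**What to change.** In Section 9.3.3, summarise serum creatinine (mean, SD, median, min, max) from the value closest to index for every patient, and compute its ASD and p-value from that value. Add one n (%) row for any high serum creatinine in the baseline period, with a laboratory limit fixed before results are seen. Keep both as candidates for the second-objective model, so that a history of high creatinine is not lost as a possible driver.

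Stating only the limit and the value to be used would make the row reproducible but would leave the mixture in the mean.

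The cost is a sentence of text, one extra table row and one correlated candidate covariate. No new data are needed. ALT, AST, total bilirubin and GFR need no change, and no rows on testing frequency are required.

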 - Carbon monoxide diffusing capacity of the lung (DLCO; n, %)

- Normal (>75% of predicted)
- Mild to moderate decrease (40-74% of predicted)
- Severe decrease (<40% of predicted)
- Oxygen saturation (n, %)
 - Normal (95-100%)
 - Below normal (<95%)
- GAP index¹⁸ (n, %), if data allow
 - Calculated using information on age, gender and FVC
 - Stage I (0-3 points)
 - Stage II (4-5 points)
 - Stage III (6-8 points)

Treatment history during the pre-index period (not including index date):

- Pharmacological interventions (n, %)
 - Other treatments (as per ATS/ERS/JRS/ALAT guidelines¹⁹)
 - Selective tyrosine kinase inhibitor against platelet derived growth factor (Imatinib)
 - Prednisone
 - Azathioprine
 - N-acetylcysteine
 - Selective endothelin receptor antagonist (ambrisentan)
 - Phosphodiesterase-5 inhibitor (sildenafil)
 - Dual endothelin receptor antagonists (macitentan, bosentan)
 - Corticosteroids
 - Inhaled corticosteroids
 - Oral corticosteroids
 - Bronchodilators
 - SABA
 - LABA
 - Anticholinergics
 - Other beta agonists
 - GERD therapy
 - H-2 receptor blockers
 - Proton pump inhibitors
 - Antacids
 - Cardiovascular drugs
 - Antianginals
 - Antihypertensives
 - Antiarrhythmics
 - Antiplatelets
 - Anticoagulants

- Antidiabetes drugs
- Anti-infectives
- Anticonvulsants
- Anti-anxiety drugs
- Antidepressants
- Antipsychotics
- Antihyperlipidemics
- Non-pharmacological interventions (n, %)
 - Surgical procedures (n, %)
 - Lung transplantation
 - Esophageal sphincter reinforcement
 - Lung cancer surgeries
 - Supportive therapy (n, %)
 - Oxygen therapy
 - Pulmonary rehabilitation
 - Diagnostic procedures (n, %)
 - High resolution computed tomography (HRCT)
 - Surgical lung biopsy
 - Chest X-rays
 - 6-minute walk test/pulmonary stress test
 - Spirometry
 - Bronchoalveolar lavage

Treatment on the index date (pharmacological interventions only):

- For each of the following treatments, the number and proportion of patients with and without the treatment on the index date will be reported (days' supply to be considered when exploring treatment use on index)
 - Other treatments (as per ATS/ERS/JRS/ALAT guidelines¹⁹; n, %)
 - Selective tyrosine kinase inhibitor against platelet derived growth factor (Imatinib)
 - Prednisone
 - Azathioprine
 - N-acetylcysteine
 - Selective endothelin receptor antagonist (ambrisentan)
 - Phosphodiesterase-5 inhibitor (sildenafil)
 - Dual endothelin receptor antagonists (macitentan, bosentan)
 - Corticosteroids (n, %)

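### FVC and DLCO are compared only in two and three categories, which shrinks a real lung-function difference below the plan's 10% line when continuous values could be used as well

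*Combined protocol and SAP*

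**What the plan says.** Section 9.3.3 of the combined protocol and SAP groups the lung-function tests under "Pulmonary function tests (PFTs) indicative of IPF severity (n", %). Within that group:

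- FVC is reported as counts and percentages in two levels, at least 80% and below 80%.
- DLCO is listed as "Carbon monoxide diffusing capacity of the lung (DLCO; n", %), in three bands. The middle band is "Mild to moderate decrease (40-74% of predicted").
- TLC alone is continuous: "Total lung capacity (TLC) (mean, SD, median, min, max").
- FEV1/FVC and oxygen saturation are each split in two.
- The GAP index is reported in stages, if data allow, and is "Calculated using information on age, gender and FVC".

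Elsewhere in 9.3.3, age, BMI and the Charlson index each have a mean, SD, median, minimum and maximum as well as categories.

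The primary outcome (9.3.2.1) is the ASD and p-value for each baseline characteristic in three pairwise cohort comparisons. Section 9.7.1 gives one ASD formula for continuous variables and one for binary proportions, "where an ASD of at least 10% will be considered a meaningful difference". It plans means and SDs "for continuous variables (e.g., age, lab measures values, BMI"). It selects model covariates by bivariate significance or face validity. "Statistical tests will be two-sided" at 0.05.

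**The concern.** The plan itself calls these tests markers of disease severity, and severity is an obvious candidate for what drives the choice of treatment. With one cut at 80%, a patient at 78% counts the same as a patient at 45%. The ASD and test then see only the share on each side of the cut.

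Three things follow if the text stands.

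- A difference that is meaningful by the plan's own 10% standard can be reported as not meaningful.
- A difference that does not change the share at or above 80% is invisible.
- Bivariate significance is one route into the logistic and propensity models, so a weakened FVC signal could also cost FVC its place there, unless it is kept on face validity.

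**Working it through.** The documents state no power or information figure for this point, so there is none to reproduce. They also give no mean, SD or share above any cut for FVC or DLCO. Every distribution below is an assumption, shown over a range.

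**FVC, cut at 80%.** Take FVC as normal with a common SD in both cohorts. Let z = (80 - mean)/SD and p = the share at or above 80%. The efficiency of the binary comparison relative to the continuous one is E = phi(z)^2 / [p(1 - p)], and the loss is 1 - E. Under the two ASD formulas in 9.7.1, a small true ASD of d appears in the binary version as about d x sqrt(E).

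| Mean | SD | z | p | E | Loss | True 0.10 shows as | True ASD needed to show 0.10 |
|---|---|---|---|---|---|---|---|
| 65 | 15 | 1.000 | 0.159 | 0.439 | 56% | 0.066 | 0.151 |
| 65 | 18 | 0.833 | 0.202 | 0.492 | 51% | 0.070 | 0.143 |
| 70 | 15 | 0.667 | 0.252 | 0.541 | 46% | 0.074 | 0.136 |
| 70 | 18 | 0.556 | 0.289 | 0.569 | 43% | 0.075 | 0.133 |
| 75 | 15 | 0.333 | 0.369 | 0.611 | 39% | 0.078 | 0.128 |
| 75 | 18 | 0.278 | 0.391 | 0.619 | 38% | 0.079 | 0.127 |

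First row worked out: phi(1) = 0.242, so E = 0.242^2 / (0.159 x 0.841) = 0.439, and 0.10 x sqrt(0.439) = 0.066. The most favourable case puts the cut at the mean (p = 0.5). There E = 2/pi = 0.637 and the loss is still 36%.

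**A difference the cut cannot see.** Here the common-SD assumption is dropped. Cohort A has mean 70, SD 15; cohort B has mean 66.7, SD 20. For A, (80 - 70)/15 = 0.667; for B, (80 - 66.7)/20 = 0.667. Both have 25% at or above 80%, so the binary ASD is 0. The continuous ASD is 3.33 / sqrt[(225 + 400)/2] = 3.33 / 17.68 = 0.19.

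**DLCO, three bands.** The cuts are taken at 40 and 75. (The printed bands stop at 74 and resume above 75, so values from just above 74 up to and including 75 have no band.) For grouped normal data, E is the sum over bands of (difference in phi at the band's two edges)^2 / (share in the band). With mean 50 and SD 15, the edges are at -0.667 and 1.667, phi is 0.3194 and 0.0995, and the shares are 0.252, 0.700 and 0.048. Then E = 0.404 + 0.069 + 0.207 = 0.68, a loss of 32%. Over means of 40-55 and SDs of 12-18 the loss runs from 25% to 47%.

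**What this could mean for the nintedanib-pirfenidone test.** Table 1 has 627 patients with an FEV/FVC value. Split in the ratio 868:615, that is 367 and 260. For an assumed true FVC difference of 0.25 SD at two-sided 0.05, power is about 87% with continuous values and 57-68% with the 80% cut (share at or above 80% from 17% to 36%). For 0.20 SD the figures are 69% and 40-49%. The split, the effect sizes and the use of 627 are all assumptions.

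**The case against.** Several points on the other side have force.

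- **Section 9.7.1 may already cover it.** It names laboratory values among its continuous variables. But the lung-function tests are a separate group marked as counts and percentages, so this does not clearly restore a continuous comparison. At best the text is ambiguous.
- **The size is not in the documents.** A reader might infer that about half the FVC information is lost as a matter of fact. That does not follow. Only the 36% floor is independent of the mean and SD, and it too needs normality with a common SD. A loss of 40-55% would require roughly 17-34% of patients at or above 80%. The DLCO loss has its own, generally smaller, range.
- **The propensity models.** A reader might infer that FVC enters them only as above or below 80%. Section 9.3.3 says how measures are reported, and 9.7.1 does not fix the coding of model covariates. The text does not support that inference.
- **Other severity measures exist.** TLC stays continuous, oxygen saturation was recorded in 1,150 patients in Table 1, and GAP stage is planned if data allow. FVC and DLCO are two of several. GAP uses FVC, but is itself reported only in stages.
- **The 627 is a weak base.** Table 1 is preliminary, covers treated patients only, counts any value before index, and labels the row FEV/FVC. It says nothing about the untreated cohort, which enters two of the three primary comparisons.
- **Missing values may matter more.** The 627 are 30% of 2,061 (row 4) or 39% of 1,623 (row 5b); the 293 DLCO values are 14% or 18%. Section 9.9 already concedes that covariates may drop out of the propensity model for missing data. Continuous model terms with no missing-data method would confine the model to that minority, whereas a categorical coding can carry a missing level. This stands, and it shapes the fix.
- **Sampling error is larger than the shrinkage.** By the formula in 9.7.1, with 367 and 260 patients the standard error of the ASD is about sqrt(627 / (367 x 260)) = 0.081, so the 95% half-width is 0.16, against a shrinkage of 0.02-0.03 at a true 0.10. True, but under this model the shrinkage always pulls towards no difference and does not fade with more patients.

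**Conclusion.** The point holds as one about how FVC and DLCO are compared in the primary analysis. As written, their ASD and p-value depend on the cuts alone, which is out of line with the plan's own treatment of age, BMI, the Charlson index and TLC.

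Under normality with a common SD, the FVC loss is at least 36%, and 38-56% for a mean of 65-75 and SD of 15-18. For DLCO it is 25-47% for a mean of 40-55 and SD of 12-18. On the same FVC assumptions the true ASD must reach about 0.13-0.15 before the plan's 10% line is met. Differences that leave the share at or above 80% unchanged are missed altogether.

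The documents do not support going further and saying that severity is missing from the plan, or that the propensity models are bound to the two-level FVC.

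**What to change.** In 9.3.3, where numeric % predicted values exist, add mean, SD, median, minimum and maximum for FVC and DLCO. State that FVC is % predicted if that is what is meant; only DLCO says so now. In 9.7.1, say that the primary ASD for these two tests uses the continuous formula with the t or Wilcoxon test, and that the categories are a descriptive display. Close the gap between the upper two DLCO bands.

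For the second objective, say how FVC and DLCO are coded if they enter the logistic or propensity models. Prefer the continuous value, with a stated method for missing values, so that the model is not restricted to the minority with a recorded test.

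The cost is two more table rows, a few sentences and a little more analysis work. It depends on numeric values being available, since the documents do not describe how the database records these tests.
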